## Clinical Investigational Synopsis

Title	Implantation with the Cochlear Nucleus® CI532 Implant Early Experience Study
Study Sites	Up to 15 study sites
Study Duration	3 months post-activation (per subject)
Study Population	Up to 50 newly implanted cochlear-implant recipients
Design Overview	The design is a within-subject, repeated-measures study. The period of participation will be 3 months postactivation. Study procedures will include mapping, speech perception, and questionnaires.
Primary Objectives	

1. To determine if unilateral listening performance at 3 months post activation with the CI532 will be superior to the best aided unilateral preoperative condition for sentence perception in quiet.

2. To determine if unilateral listening performance at 3 months post activation with the CI532 will be superior to the best aided unilateral preoperative condition for sentence perception in noise.

Primary Endpoints	

1. Sentence perception in quiet will be superior for subjects implanted with the CI532 when compared to their preoperative best aided unilateral listening condition.

2. Sentence perception in noise will be superior for subjects implanted with the CI532 when compared to their preoperative best aided unilateral listening condition.

Additional Information	

1. To quantify the change in audiometric threshold (125 – 750 Hz) at 3 months postactivation when compared to the preoperative period

Study Intervals	Primary data points are at 3 months post-activation.

---

CONFIDENTIAL

March 31, 2016

CAM-CL-027\_PRT

Rev. 1

Page 5 of 21

## Abbreviations

Term	Definition
AE	Adverse Event
CRF	Case Report Form
IA	Initial Activation
IRB	Institutional Review Board
SAE	Serious Adverse Event
SNR	Signal to noise ratio
S 0 N 90	Speech presented at 0 degrees azimuth and background noise presented from the side of the implant

---

CONFIDENTIAL

March 31, 2016

CAM-CL-027\_PRT

Rev. 1

Page 6 of 21

## 1. Introduction

Cochlear implantation is an FDA and Health Canada approved treatment for sensorineural hearing loss. Nucleus cochlear implants are indicated for individuals who demonstrate minimal benefit from appropriately fit hearing aids. Audiometrically, adults must possess a bilateral moderate to profound sensorineural hearing loss and children must possess a severe to profound sensorineural hearing loss. A common hypothesis in peer reviewed literature is that performance outcomes with cochlear implants depend critically on the placement of the electrode array within the cochlea.

A cochlear implant is composed of two main components: a receiver stimulator and an electrode array. Electrode array designs are typically either lateral wall or peri-modiolar hugging. A lateral wall electrode is a straight electrode design that, when inserted into the cochlea, hugs the outer wall of the cochlea, with final position *lateral* to the modiolus. A perimodiolar electrode is a pre-curved electrode design, held straight for insertion purposes, but as inserted into the cochlea curves to mimic the curvature of the modiolus, with final position medial to the modiolus. Electrode placement closer to the modiolus has been documented to improve performance outcomes in traditional cochlear implant candidates (Holden et al. 2013; van der Beek et al. 2005).

In addition to medial and lateral placement, there are also scala considerations within the cochlea. The cochlea is divided into three scala: scala media, scala tympani and scala vestibuli. Holden et al (2013), Finley et al. (2008), Aschendorff et al. (2007), Skinner et al. (2007) as well as other peer reviewed publications have demonstrated that electrode arrays located within scala tympani, as opposed to scala vestibuli, are often correlated with higher speech perception scores. Due to the location of ganglion cells within the modiolus, it has been suggested that there is a higher potential for electrodes in scala vestibuli to stimulate more than one turn of the cochlea, potentially causing cross-turn stimulation, pitch confusions and therefore diminished speech recognition (Finley et al. 2008).

The device proposed for study is the Nucleus® CI532 cochlear implant which consists of a CI500 Series receiver/stimulator and a pre-curved, modiolar electrode array (EA32). Individuals who will be recruited for participation in this study will be required to meet commercial cochlear implant indications. The study will compare the performance outcomes at 3 months postactivation with the best aided preoperative performance outcomes using a within subject study design. Up to 15 clinical study sites will be asked to participate with up to 50 subjects implanted.

---

CONFIDENTIAL

March 31, 2016

CAM-CL-027\_PRT

Rev. 1

Page 7 of 21

## **2. Study Objectives**

### **2.1 Primary Objectives:**

- 1) To determine if performance at 3 months post activation with the CI532 is superior to the best aided unilateral preoperative condition for sentence perception in quiet.
- 2) To determine if performance at 3 months post activation with the CI532 is superior to the best aided unilateral preoperative condition for sentence perception in noise.

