### **2.2 Primary Endpoints:**

- 1) Sentence perception in quiet will be superior for subjects implanted with the CI532 when compared to their preoperative best aided unilateral listening condition.
- 2) Sentence perception in noise will be superior for subjects implanted with the CI532 when compared to their preoperative best aided unilateral listening condition.

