## 7. Investigational Procedures

### 7.1 Design Overview

The Implantation with the Cochlear Nucleus® CI532 Implant - Early Experience Study will be conducted as a multi-center, prospective, single-arm clinical study, evaluating the safety and functionality of the Cochlear Nucleus CI532 cochlear implant in up to 50 subjects who meet current cochlear implant indications. A single-subject repeated-measures analysis will be employed whereby subjects will act as their own control. A single-subject research design is appropriate since it accommodates the heterogeneity that characterizes hearing-impaired populations. Blinding procedures are not appropriate for this trial design, as it is not possible to conceal the presence, or absence, of a cochlear implant from device recipients and/or clinical investigators.

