### 7.2 Description of Test Measures

#### 7.2.1 Clinical Audiological Testing

Subjects will undergo a standard battery of audiological tests. Audiological data will be gathered pre-operatively, at Initial Activation (IA) and at 3-months post IA.

The clinical data gathered for this study will include:

- 1) Tympanometry, both ears.
- 2) Frequency-specific thresholds at standard audiometric frequencies for both ears.
  - a) Air conduction: 125, 250, 500, 750, 1000, 2000, 3000, 4000, and 8000 Hz
  - b) Bone conduction: 250, 500, 1000, 2000, 3000 and 4000 Hz
- 3) Aided speech recognition in quiet: AzBio sentences (Spahr et al., 2012) presented at 60 dBA in the sound field for the unilateral listening ear.
  - a) Sentence testing in quiet will only be conducted in subjects aged 12 years and older
- 4) Aided speech recognition in noise: AzBio sentences (Spahr et al., 2012) using speech weighted noise presented at 65 dBA with a +5 dB signal to noise ratio spatially separated, speech 0 degrees azimuth and noise 90 degrees towards the implanted ear.
  - a) Sentence testing in noise will only be conducted in subjects aged 12 years and older.

Note: The contralateral ear will be plugged/muffed for all audiological testing.

---

CONFIDENTIAL

March 31, 2016

CAM-CL-027\_PRT

Rev. 1

Page 11 of 21

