## 7.3 Preoperative Procedures

### 7.3.1 Visit 1

A baseline evaluation will be conducted to measure the subject's preoperative, best aided, unilateral listening performance pre-surgery. The following audiological testing will be completed:

- 1) Tympanometry, both ears.
- 2) Frequency-specific thresholds at standard audiometric frequencies for both ears.
  - a) Air conduction: 125, 250, 500, 750, 1000, 2000, 3000, 4000, and 8000 Hz
  - b) Bone conduction: 250, 500, 1000, 2000, 3000 and 4000 Hz
- 3) Aided speech recognition in quiet: AzBio sentences (Spahr et al., 2012) presented at 60 dBA in the sound field for the unilateral listening ear.
  - a) Only to be collected on subjects aged 12 years and older.
- 4) Aided speech recognition in noise: AzBio sentences (Spahr et al., 2012) using speech weighted noise presented at 65 dBA with a +5 dB signal to noise ratio spatially separated, speech 0 degrees azimuth and noise 90 degrees towards the implanted ear for the unilateral listening ear.
  - a) Only to be collected on subjects aged 12 years and older.

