## 7.5 Postoperative Procedures

### 7.5.1 Visit 3

At the initial activation appointment, the following procedures will be completed:

---

CONFIDENTIAL

March 31, 2016

CAM-CL-027\_PRT

Rev. 1

Page 12 of 21

Cochlear

- 1) Tympanometry, both ears.
- 2) Frequency-specific thresholds at standard audiometric frequencies for both ears.
  - a) Air conduction: 125, 250, 500, 750, 1000, 2000, 3000, 4000, and 8000 Hz
  - b) Bone conduction: 250, 500, 1000, 2000, 3000 and 4000 Hz
- 3) The initial activation will be performed according to standard clinical procedures using Custom Sound and the default programming settings for the Nucleus 6 sound processor.
  - a) Impedances and NRT are to be measured.
  - b) An anonymous .cdx file will be provided to the study sponsor.
- 4) Audiologist Questionnaire will be completed for each subject.

#### 7.5.2 Visit 4

At 3 months postactivation, the following procedures will be completed:

- 1) Tympanometry, both ears.
- 2) Frequency-specific thresholds at standard audiometric frequencies for both ears.
  - a) Air conduction: 125, 250, 500, 750, 1000, 2000, 3000, 4000, and 8000 Hz
  - b) Bone conduction: 250, 500, 1000, 2000, 3000 and 4000 Hz
- 3) Aided speech recognition in quiet: AzBio sentences (Spahr et al., 2012) presented at 60 dBA in the sound field for the unilateral listening ear.
  - a) Only to be collected on subjects aged 12 years and older.
- 4) Aided speech recognition in noise: AzBio sentences (Spahr et al., 2012) using speech weighted noise presented at 65 dBA with a +5 dB signal to noise ratio spatially separated, speech 0 degrees azimuth and noise 90 degrees towards the implanted ear for the unilateral listening ear.
  - a) Only to be collected on subjects aged 12 years and older.
- 5) Mapping will be performed according to standard clinical procedures using Custom Sound and the default programming settings for the Nucleus 6 sound processor.
  - a) Impedances and NRT are to be measured.
  - b) An anonymous .cdx file will be provided to the study sponsor.

---

CONFIDENTIAL

March 31, 2016

CAM-CL-027\_PRT

Rev. 1

Page 13 of 21

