## **10. Data Analysis**

### **10.1 Statistical Analysis**

All subjects who are consented into the clinical study will constitute the intention-to-treat (ITT) population for the purposes of safety evaluation. Only subjects implanted with the CI532 and completed per the protocol will be considered as the completed cases (CC) population and per protocol (PP).

Demographic and outcomes data will be tabulated individually along with group summary descriptive statistics. Speech perception scores will be presented for each study evaluation, pre- and postoperatively, so that postoperative progress can be evaluated over time.

Performance with the Nucleus CI532 will be determined by a comparison of preoperative, best aided, ear to be implanted vs. 3 months postactivation outcome measures. The speech perception measures chosen for this purpose are the AzBio sentences in both quiet and noise in the unilateral listening condition.

The primary study endpoints will be statistically significant differences between the mean, preoperative speech perception scores and postoperative scores for the activated, CI532 cochlear implant subjects who completed speech perception testing. Mean scores as measured by AzBio sentences in quiet and noise will be compared. The null hypothesis to be tested is that there is no difference for the subjects between their pre- vs. postoperative speech performance

Individual scores obtained at 3 months will be compared with those obtained, on the same measures preoperatively, based on the binomial model where appropriate (see Thornton and Raffin, 1978; Boothroyd and Nittrouer, 1988). Although the binomial model is the more appropriate statistical model for analysis of single-subject experimental data, conventional group-based statistics will also be applied to the pooled results. For all of the speech perception measures, nonparametric procedures (e.g., a Signed-Ranks test) will be conducted in order to further confirm the results of the single-subject analyses. These tests will be two-tailed and applied using an alpha level of 0.05.

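### Is the preoperative comparator for the primary endpoints left open as to which ear is tested?

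*Protocol*

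**What the plan says.** The comparator is described in several places, at different levels of detail.

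- **Synopsis, primary objectives:** "unilateral listening performance at 3 months post activation with the CI532 will be superior to the best aided unilateral preoperative condition". No ear is named.
- **Section 2.1:** the CI532 result is to be "superior to the best aided unilateral preoperative condition for sentence perception in quiet", with a parallel objective for noise. No ear is named.
- **Section 2.2:** the endpoints hold "when compared to their preoperative best aided unilateral listening condition". No ear is named.
- **Section 7.3.1 (Visit 1):** the baseline measures "preoperative, best aided, unilateral listening performance pre-surgery". AzBio sentences are given once in quiet and once in noise to a unilateral listening ear that is not defined.
- **Section 7.5.2 (Visit 4):** the noise test is set up with "noise 90 degrees towards the implanted ear for the unilateral listening ear", the same set-up as at Visit 1.
- **Section 7.2.1:** "The contralateral ear will be plugged/muffed for all audiological testing".
- **Section 10.1:** performance is determined by "a comparison of preoperative, best aided, ear to be implanted vs. 3 months postactivation outcome measures". This is the only place where the comparator is tied to a named ear.
- **SAP:** it opens by referring to protocol Section 10.1 and restates the endpoint as a difference in mean scores, without naming an ear.

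**The concern.** The phrase best aided unilateral has two natural readings. It can mean the ear to be implanted, tested with the best available aiding, or it can mean whichever single ear performs best when aided. The one section that settles this is the statistics section, whereas site staff work from Section 7. There the test ear is undefined, and the plugging note does not say which ear the plugged one is contralateral to.

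The score is the baseline for both primary endpoints. Only one AzBio score per condition is scheduled before surgery, so if a site tested the other ear there would be no same-ear score to fall back on, and it could not be collected later. With up to 15 sites, a mixed reading would pool within-ear changes with between-ear differences. In noise the geometry would differ too: the noise would face the plugged ear at baseline and the listening ear at 3 months. The individual binomial comparisons in Section 10.1 and the SAP would also lose their meaning for those subjects, because the two scores would not be repeats of one measure.

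**Working it through.** **1. Does any section define a different comparator?**

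| Place | Ear named for the comparator |
|---|---|
| Synopsis, Sections 2.1 and 2.2 | none |
| Section 7.3.1 | none (unilateral listening ear) |
| Section 10.1 | ear to be implanted |
| SAP | none, but refers to Section 10.1 |

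One place is specific and the others are silent. None names the better ear or the non-implanted ear, so the sections differ in detail without contradicting each other.

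**2. Does Section 10.1 govern the looser term?** After naming the ear to be implanted, it says in the next sentence that the measures for this purpose are AzBio in quiet and noise in the unilateral condition. The two terms describe the same measure.

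**3. What do the test instructions imply?**

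- At Visit 4 the unilateral listening ear must be the implanted one, since the synopsis concerns unilateral performance with the CI532.
- Visit 1 uses the same term and the same loudspeaker set-up, and Section 10.1 compares scores on the same measures before and after surgery. The same term should therefore mean the same ear.
- Section 7.1 states that "subjects will act as their own control", which in a unilateral test calls for like-for-like measurement.
- The abbreviations list places the noise on the side of the implant. A site taking the better-ear reading would have to aim the noise at a plugged ear.
- In Section 7.2.1 the last specific ear mentioned before the plugging note is the implanted ear.

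**4. What would a misreading cost?** Section 10.2 gives 23 evaluable subjects for at least 90% power at one-sided 0.025 with a paired t-test. The mean and SD behind it are not stated, so the 23 can only be back-solved. With the noncentral t distribution on 22 degrees of freedom and noncentrality d√23, the smallest standardised change giving 90% power is d = 0.7075. That d returns 18, 23, 14 and 19 for the four scenarios, against the stated 18, 23, 16 and 20. It fits the 0.025 rows and only approximates the 0.05 rows.

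Suppose a share p of subjects had a better-ear baseline higher by s, in SDs of the paired change. Both p and s are assumptions. Then

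effect = (0.7075 − p·s) / √(1 + p(1 − p)s²).

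For example, with p = 0.25 and s = 0.2: (0.7075 − 0.05) / √(1 + 0.1875 × 0.04) = 0.6575 / 1.0037 = 0.655, which gives 85.1% power at n = 23.

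| Evaluable n | Share p | s = 0.1 | s = 0.2 | s = 0.3 |
|---|---|---|---|---|
| 23 | 0.25 | 87.8% | 85.1% | 82.0% |
| 23 | 0.5 | 85.3% | 79.1% | 71.5% |
| 23 | 1 | 79.5% | 64.3% | 46.4% |
| 35 | 0.25 | 97.5% | 96.4% | 95.0% |
| 35 | 1 | 93.7% | 83.1% | 64.9% |

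Unshifted power is 90.0% at n = 23 and 98.2% at n = 35. The n of 35 is illustrative. Section 10.2 allows up to 50 subjects but raises the number partly to include children who cannot do the test, so the evaluable number is unknown.

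**5. Direction.** A better-ear baseline would be higher than a same-ear one, and noise facing the plugged ear would make the baseline noise test easier still. Both shrink the apparent gain, so a misreading would make a positive result harder to reach.

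**The case for a change.** The strongest opposing case is that the only clear definition sits where site staff are least likely to look. The loudspeaker direction fixes the source of the noise but not the ear under test. The plugging note names no reference ear. The SAP does not carry the definition forward in its own words. The baseline cannot be repeated after surgery, and the remedy is cheap: copy the Section 10.1 wording into the other sections and check the tested ear on the source worksheets.

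The textual observations are correct, and consistent wording would read better. The step from there to a defect does not stand. Nothing in the documents shows a baseline taken in the wrong ear. The CRFs, worksheets and CRF completion instructions are not in the public documents, so the absence of a field for the tested ear cannot be inferred. The low-power entries need every subject to be tested in the other ear together with the larger assumed shifts. The SAP, dated January 2018, describes the primary comparison largely in the past tense, so new protocol wording could not alter baselines already taken. A baseline in the other ear would also depart from the comparator in Section 10.1, and that section limits the completed-cases and per-protocol populations to subjects who completed per the protocol.

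**Conclusion.** The concern does not call for a change. The wording is uneven, but the plan contains one definition of the comparator, in the section that governs the analysis, and no competing one. Following the plan as written gives a sound comparison of the same ear before and after implantation.

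The harm depends on two quantities absent from the documents: the share of subjects tested in the other ear and the size of the difference between ears. If a quarter were affected, the loss at n = 23 would be about 2 to 8 percentage points of power (90.0% to between 87.8% and 82.0%), and at n = 35 about 1 to 3 points (98.2% to between 97.5% and 95.0%). These figures rest on the back-solved d = 0.7075 and on shifts of 0.1 to 0.3 SD. The bias would run against the device. No stated sample size, alpha level or decision rule is shown to be wrong. The result should be read as improvement over the same ear's aided preoperative score, which is what Section 10.1 says.

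This conclusion would change only if source records showed that baselines had in fact been taken in the other ear.

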### **2.2 Primary Endpoints:**

- 1) Sentence perception in quiet will be superior for subjects implanted with the CI532 when compared to their preoperative best aided unilateral listening condition.
- 2) Sentence perception in noise will be superior for subjects implanted with the CI532 when compared to their preoperative best aided unilateral listening condition.

## **3. Study Design**

The design is a within-subject, repeated-measures clinical investigation.

## **4. Study Length**

The duration of the study for each subject is 3 months post-activation.

## **5. Device Description**

The cochlear implant system that will be used in this study comprises:

- Nucleus® CI532 Cochlear Implant
- Nucleus 6 (CP900 series) Sound Processor, and
- Nucleus Custom Sound™ programming software.

### **5.1 Implant Description**

The commercially available Cochlear Nucleus CI532 cochlear implant will be used in this study.

---

CONFIDENTIAL

March 31, 2016

CAM-CL-027\_PRT

Rev. 1

Page 8 of 21

Figure 1. Nucleus CI532 cochlear implant.

## 5.2 Sound Processor Description

The commercially available Nucleus 6 sound processor will be used in this study.

Figure 2. Nucleus 6 (CP900 series) sound processor.

---

CONFIDENTIAL

March 31, 2016

CAM-CL-027\_PRT

Rev. 1

Page 9 of 21

### **5.3 Programming Software Description**

The commercially available programming software, Custom Sound, will be used in this study.

## **6. Subject Population**

### **6.1 Inclusion Criteria**

- Medical and audiological candidate for a CI532 cochlear implant per commercially approved, age appropriate, FDA indications
- Post-linguistically deafened
- Ability to complete age appropriate testing

### **6.2 Exclusion Criteria**

- Previous cochlear implantation in the ear to be implanted
- Pre-linguistically deafened (onset of hearing loss at less than two years of age)
- Women who may be pregnant at the time of cochlear implant surgery
- Ossification or any other cochlear anomaly that might prevent complete insertion of the electrode array
- Diagnosis of retro-cochlear pathology
- Diagnosis of auditory neuropathy
- Unrealistic expectations on the part of the subject regarding the possible benefits, risks, and limitations that are inherent to the surgical procedure and use of the prosthetic device
- Unwillingness or inability to comply with all investigational requirements
- Additional cognitive handicaps that would prevent participation on all study requirements

### **6.3 Release of Medical Information**

Subjects will be required to release the exchange of medical information between the Investigator(s) and the Sponsor. This requirement will be clearly identified in the Informed Consent form.

---

CONFIDENTIAL

March 31, 2016

CAM-CL-027\_PRT

Rev. 1

Page 10 of 21

